2. LIST OF ABBREVIATIONS

Abbreviation	Definition
ATTR	Transthyretin Amyloidosis
ATTR-ACT	Tafamidis Treatment Study for Patients with Transthyretin Amyloid Cardiomyopathy
ATTR-CM	Transthyretin cardiac amyloidosis
ATTR-PN	Transthyretin amyloidosis with polyneuropathy
ATTRv	Hereditary transthyretin amyloidosis
ATTRwt	Natural or wild-type transthyretin amyloidosis
CCE	Conductance Cutaneous Electrochemistry
CNS	Central nervous system
COMPASS-31	Composite Autonomic Symptom Score 31
CV	Cardiovascular
CVR-R	Coefficient of Variation of the R-R interval
eGFR	Estimated Glomerular Filtration Rate
EMG	Electromyogram
HF	Heart failure
LTE	ATTR-ACT Long-term Extension Study
mBMI	Modified body mass index
NCS	Nerve conduction studies
NIS	Neuropathy Impairment Score
NIS-LL	Neuropathy Impairment Score Lower Limbs
Norfolk QoL-DN	Norfolk Quality of Life-Diabetic Neuropathy

PFIZER CONFIDENTIAL

PN	Polyneuropathy
PND	Polyneuropathy Disability Score
QoL	Quality of Life
SCR	Sympathocutaneous response
TTR	Transthyretin

4. ABSTRACT

Title: “Tafamidis 61mg, Outcomes in ATTR Amyloidosis with Neurological and Multisystemic Involvement - TRAMA.” B3461104

Hypotheses and Objectives: Tafamidis free acid 61 mg has been shown (compared to placebo) to reduce the combination of all-cause mortality and the frequency of cardiovascular-related (CV) hospitalizations, as well as to slow the decline in functional capacity and quality of life (QoL) of patients with ATTR-CM of hereditary or wt origin. In this study the hypothesis is that tafamidis free acid 61 mg reduces the progression of neurological variables in ATTRv and ATTRwt patients with neurologic involvement.

The objective of the study is to conduct a retrospective study to evaluate the efficacy of tafamidis 61 mg on non-cardiac variables in patients with ATTRv and ATTRwt, included in the ATTR-ACT (B3461028) and/or LTE (extension study) studies (B3461045) in Spain, with a minimum neurological follow-up of 12 months. In addition, these populations will be described.

EVALUATING IEC: PPD [REDACTED]

Sponsor: PPD [REDACTED]

- Protocol Version 1.0. Date: February 17, 2022

Contact person: PPD [REDACTED]. Sr. Medical Advisor Pfizer S.L.U.

5. AMENDMENTS AND UPDATES

Not applicable

CCI [REDACTED]

[REDACTED]	[REDACTED]

PFIZER CONFIDENTIAL

[REDACTED]

CCI	
	022

7. RATIONALE AND BACKGROUND

Transthyretin amyloidosis (ATTR) is a rare, progressive, clinically heterogeneous, and life-threatening disease caused by pathogenic mutations in the transthyretin (*TTR*) gene, resulting in the hereditary form (ATTRv), or due to factors related to aging, resulting in the natural or wild-type form (ATTRwt) of the disease. (Adams D, et al; Nativi Nicolau JN, et al)^{1,2}

ATTR is a systemic disease in which deposition of TTR amyloid insoluble fibers can occur in multiple tissues, including the peripheral nervous system, heart, kidneys, gastrointestinal tract, and eyes, resulting in, as most common phenotypes, peripheral and/or autonomic polyneuropathy (ATTR-PN), restrictive cardiomyopathy (ATTR-CM), or a mixed phenotype (Adams D, et al)¹. More than 140 mutations in the *TTR* gene have been described, with different phenotypes based on the mutation that the patient has (Adams D, et al)¹. However, with disease progression, unique phenotypes generally become mixed phenotypes where cardiomyopathy can be accompanied by polyneuropathy and vice versa. In the case of ATTRwt, although the disease usually manifests with cardiac symptomatology, patients may present with sensory-motor and autonomic neurological disturbances, which in any case are less prominent in the clinical condition (Nativi Nicolau JN, et al)².

Cardiac transthyretin amyloidosis (ATTR-CM) is caused by extracellular deposition of TTR amyloid fibers in the heart, both in the ATTRwt form and in the ATTRv form, resulting in restrictive cardiomyopathy that clinically manifests as heart failure (HF) (Ruberg FL, et al)³. At least 22 mutations associated with ATTR-CM have been described, with Val122Ile, Thr60Ala, Leu111Met and Ile68Leu being the most common mutations (Rowczenio DM, et al; Caponetti AG, et al; González-Moreno J, et al)⁴⁻⁶.

Globally, the inherited form of the disease can occur in both endemic and non-endemic areas. In Spain at the national level, there are two endemic foci where the prevalence of the disease is higher: Palma de Majorca and Huelva. There is currently little information on the clinical profiles of patients in Spain. The majority of the information is from endemic areas, while data from non-endemic areas remains scarce (González-Moreno J, et al; Silva Hernández, et al; Álvarez-Rubio J, et al.)⁶⁻⁸. Regarding neurologic involvement in ATTRwt patients, few descriptive and prevalence data are published internationally and all point to the need for a multidisciplinary

approach at follow-up ([González-Moreno J, et al](#); [Kharoubi M, et al](#); [Wajnsztajn Yungher F, et al](#); [Russell A, et al](#); [Papagianni A, et al](#); [Kleefeld F, et al](#))^{5,9-13}.

Recently published data on the demographics and clinical characteristics of clinically overt Spanish patients from the Transthyretin Amyloidosis Outcomes Survey (THAOS), a global, multicenter, longitudinal, observational survey of ATTR patients and asymptomatic carriers, shows phenotypic heterogeneity associated with this disease in Spain ([González-Moreno J, et al](#))⁶. Specifically, for patients carrying the Val122Ile variant, only 20% had a purely cardiac phenotype, while many had a neurological phenotype (40%) or mixed phenotype (40%). On the other hand, most patients with ATTRwt had a mixed phenotype (64.9%), whereas only one third had purely cardiac (22.8%) or neurological (12.3%) phenotype. The results of this analysis highlight the importance of a multidisciplinary approach and the need for a comprehensive neurological and cardiological assessment in both ATTRv and wt patients ([González-Moreno J, et al](#))⁶.

Tafamidis is a benzoxazole derivative without nonsteroidal anti-inflammatory activity that binds to TTR thyroxine binding sites with high affinity and selectivity. This leads to inhibition of dissociation of TTR tetramer into monomers, preventing the formation of amyloid fibers ([Bulawa CE, et al](#))¹⁴. Tafamidis 20 mg has been shown to slow the progression of peripheral neurological deterioration in patients with ATTR polyneuropathies (ATTR-PN) at stage 1 ([Coelho T, et al](#))¹⁵ and has been approved in Spain since 2011 for the treatment of transthyretin amyloidosis in adult patients with stage 1 polyneuropathy to delay peripheral neurological impairment (Information available on [AEMPS](#))¹⁶.

In the clinical trial to evaluate the safety and efficacy of tafamidis in transthyretin cardiac amyloidosis (ATTR-ACT), tafamidis at a dose of 20 mg and 80 mg (4 x 20 mg) was shown (compared to placebo) to reduce the combination of all-cause mortality and the frequency of cardiovascular-related (CV) hospitalizations, as well as to slow down the decline in functional capacity and quality of life (QoL) of patients with ATTR-CM of hereditary origin or wt ([Maurer MS, et al](#))¹⁷. Based on these outcomes, tafamidis obtained FDA and EMA approval for the treatment of patients with ATTR-CM (Information available at: [AEMPS; FDA](#))^{18,19}.

Upon completion of the ATTR-ACT study, patients had the option to participate in the extension study, LTE ([NCT02791230](#))²⁰ (B3461045), in which patients could be treated with tafamidis for an additional 60 months ([Damy T, et al](#))²¹. In the LTE, patients who in the ATTR-ACT study received tafamidis continued to receive the same dose, while patients who received placebo were randomly reassigned to receive tafamidis 80 mg or 20 mg at a 2:1 ratio. Following the July 20, 2018 protocol addendum, all patients were switched to 61 mg of tafamidis free acid, a new single capsule formulation that is bioequivalent to 80 mg of tafamidis meglumine used in the ATTR-ACT ([Lockwook PA, et al](#))²². Published outcomes show that tafamidis 80 mg/61 mg has greater efficacy by reducing all-cause mortality by 30% versus tafamidis 20 mg ([Damy T, et al](#))²⁰.

In a retrospective study conducted in 210 patients with ATTRv in treatment with tafamidis 20 mg and with a follow-up of 18-66 months, it was observed that patients classified as non-responders had lower drug concentrations. The outcomes of this study support the hypothesis that ATTRv patients with polyneuropathy may benefit from a higher dose of tafamidis (Monteiro C, et al)²³.

Due to the phenotypic heterogeneity of ATTR patients and the growing demand for real-world data on the effect of tafamidis 61 mg in patients with systemic involvement, our objective is to conduct a retrospective study to evaluate the efficacy of tafamidis 61 mg in non-cardiac variables in patients with ATTRv and ATTRwt, included in the ATTR-ACT (B3461028) and LTE (B3461045) in Spain. To do this, extra-cardiac clinical data will be collected throughout the follow-up and treatment period with tafamidis 61 mg, in order to evaluate the efficacy of treatment in ATTR patients with neurologic involvement.

To date, little information has been published on the demographic and clinical characteristics of clinically overt Spanish ATTR patients (González-Moreno J, et al; Silva Hérnandez, et al; Álvarez-Rubio J, et al.)⁶⁻⁸, and even less international data have been published on neurologic involvement in ATTRwt patients (González-Moreno J, et al; Kharoubi M, et al; Wajnsztajn Yungher F, et al; Russell A, et al; Papagianni A, et al; Kleefeld F, et al)^{6, 9-13}. In addition, this study will provide an overview of Spanish patients with mixed phenotype and provide real-world data on the deterioration of polyneuropathy and management of ATTRwt patients.

There is currently no published data on the use of tafamidis free acid 61 mg in patients with ATTR-PN, therefore this study addresses an unmet medical need and may yield on the efficacy of tafamidis free acid 61 mg in patients with mixed phenotype ATTRv and in ATTRwt patients with neurologic involvement.

8. RESEARCH QUESTION AND OBJECTIVES

Based on the outcomes from previous studies (Coelho T, et al; Maurer MS, et al)^{15,17}, the hypothesis of the present study is that tafamidis free acid 61 mg decreases the progression of polyneuropathy caused by transthyretin amyloidosis in ATTRv and ATTRwt patients with neurological or mixed phenotype.

The study's primary objective is:

- To determine the efficacy of tafamidis free acid 61 mg in ATTRv patients with neurologic involvement included in studies B3461028 and/or LTE (B3461045) in Spain through changes in the NIS scale at 12 months.

The **secondary objectives** of this study are:

- To determine the efficacy of tafamidis 61 mg in ATTRv patients with neurologic involvement included in studies B3461028 and/or LTE (B3461045) in Spain using additional non-cardiac variables at 6, 12, 18, 24 and 36 months after the start of treatment.
- To determine the efficacy of tafamidis free acid 61 mg in ATTRwt patients with neurological symptoms included in studies B3461028 and/or LTE (B3461045) in Spain, through non-cardiac variables at 6, 12, 18, 24 and 36 months after treatment initiation.
- To describe the extra-cardiac characteristics of ATTRv and ATTRwt patients included in studies B3461028 and/or LTE (B3461045) in Spain with mixed phenotype treated with tafamidis free acid 61 mg.

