9. RESEARCH METHODS

9.1. Study design

Retrospective, multicenter, non-interventional, observational and descriptive study.

It will by no means interfere with the investigator's decision on the most appropriate medical care or treatment for the patient or carrier.

The variables collected are consistent with the objectives of the study and will be described in more detail in Section 9.3:

Primary objective	Primary variables
To determine the efficacy of tafamidis free acid 61 mg in ATTRv patients with neurologic involvement included in studies B3461028 and/or LTE (B3461045) in Spain through changes in the NIS scale at 12 months.	Neuropathy Impairment Score (NIS)
Secondary objectives	Secondary variables
To determine the efficacy of tafamidis 61 mg in ATTRv patients with neurologic involvement included in studies B3461028 and/or LTE (B3461045) in Spain using additional non-cardiac variables at 6, 12, 18, 24 and 36 months after the start of treatment.	
 - NIS at 6, 18, 24 and 36 months - NIS-LL, Norfolk QoL-DN, COMPASS-31 and FAP-RODs, FAP - % of patients who do not have stage progression in the PND score

PFIZER CONFIDENTIAL

	
 - % of patients responding to treatment (defined as <4p in NIS and <2p in NIS-LL) - R-R Range Variability - mBMI - Amplitude of the potentials measured in sural sensory and ulnar, tibial and peroneal motor NCS

To determine the efficacy of tafamidis free acid 61 mg in ATTRwt patients with neurological symptoms included in studies B3461028 and/or LTE (B3461045) in Spain, through non-cardiac variables at 6, 12, 18, 24 and 36 months after treatment initiation.
	
 - NIS, NIS-LL, Norfolk QoL-DN, COMPASS-31 and FAP-RODs, FAP - % of patients who do not have stage progression in the PND score - % of patients responding to treatment (defined as <4p in NIS and <2p in NIS-LL) - R-R Range Variability - mBMI. - Amplitude of the potentials measured in sural sensory and ulnar, tibial and peroneal motor NCS

To describe the extra-cardiac characteristics of ATTRv and ATTRwt patients included in studies B3461028 and/or LTE (B3461045) in Spain with mixed phenotype treated with tafamidis free acid 61 mg.
	
 - Demographic variables - Age of onset symptoms and at diagnosis - Neurological and extra-cardiac clinical variables

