3.2.1 Primary objective

The study's primary objective is:

- To determine the efficacy of Tafamidis free acid 61 mg in ATTRv patients with neurologic involvement included in studies B3461028 and/or LTE (B3461045) in Spain through changes in the NIS scale at 12 months (See B3461104_Archive Note).

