4 STUDY POPULATION

The current study population consists of ATTRv and ATTRwt patients who have participated in studies B3461028 and B3461045 in Spain, with cardiac and neurologic involvement receiving or who have received Tafamidis free acid 61 mg for at least 12 months, and who are in neurological follow-up for no less than 12 months. According to the protocol, patients who meet the inclusion criteria are estimated to be: 10 with ATTRv and 10 with ATTRwt.

Individuals participating in the TRAMA study must meet all of the inclusion and none of the exclusion criteria.

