6 METHODS FOR THE STATISTICAL ANALYSIS

The analysis methods to be used to achieve the study objectives and draw up the descriptive content for the variables are detailed below.

❖ UNIVARIATE ANALYSIS

Quantitative variables will be described with centralization and scattering measures (mean, SD (standard deviation), median, minimum, maximum, Q1 (first quartile), Q3 (third quartile and N).

Qualitative variables will be described by absolute and relative frequencies. Two columns of percentages will be presented: Total Percentage (Total %) and Valid Percentage (Valid %):

- Total Percentage (%): Percentage of the sum of valid responses plus missing values, i.e. of the total of the sample under study.
- Valid percentage (Valid %): Percentage of total valid responses, i.e. with data on the variable.

In subgroup analyses, only the valid % with respect to the total for each group will be presented.

For questions with more than one answer option, **multiple response** tables will be shown. Two percentage column will be shown in these tables:

- Total percentage (%) Percentage of the sum of valid responses plus missing values, i.e. of the total of the sample under study. Since it is multiple choice, the sum of percentages does not have to be 100 (the percentage may be exceeded).
- Valid percentage (%) Percentage of the number of patients with at least one given answer from among the possible answers. Since it is multiple choice, the sum of percentages does not have to be 100 (the percentage may be exceeded).

Missing data will not be attributed and will be left as lost data.

Statistical analysis of variables collected in the study will be performed using the SPSS statistical program.

NOTE 1: Due to the small number of patients available in the study, no comparisons will be made and the associated p-value will not be shown. Only descriptive analyses will be presented.

NOTE 2: The texts collected in open fields will not be grouped, other than to standardize format and spelling. If desired, any grouping must be performed by the sponsor and as an additional table to the description of what is included in the database.

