12 ANALYSIS OF THE OBJECTIVES

12.1 Primary objective

“To determine the efficacy of Tafamidis free acid 61 mg in ATTRv patients with neurologic involvement included in studies B3461045 and/or LTE (B3461045) in Spain through changes in the 12-month NIS scale”

Primary variable: Neuropathy Impairment Score (NIS).

NOTE: ATTRv patients are considered to be those who have indicated “Mutation” in the genotype (Data related to the disease at diagnosis).

See resolution of this objective in 10.3.1 (month 12).

Additionally, the results will be presented for the percentage of patients responding to treatment of the change at month 12 with respect to the initial value. The N and % of patients responding to treatment will be calculated, defining responder as:

- change at 12 months compared to the initial data <4p in NIS, patients who have obtained less than 4 points in the NIS in month 12

Patients who do not meet the previous condition will be considered non-responders. If complete data is not available, the value will be left as missing.

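### The plan aims to determine efficacy and slowed progression, but gives no workable reference against which to judge the Month-12 NIS result

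*Protocol*

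**What the plan says.** - **Hypothesis and objective.** Protocol section 8, repeated in SAP 3.2, is directional: "the hypothesis of the present study is that tafamidis free acid 61 mg decreases the progression of polyneuropathy caused by transthyretin amyloidosis". SAP 3.2.1 gives the primary objective as "To determine the efficacy of Tafamidis free acid 61 mg in ATTRv patients with neurologic involvement", judged, in Protocol section 8, "in Spain through changes in the NIS scale at 12 months".
- **Design.** Protocol 9.1: "Retrospective, multicenter, non-interventional, observational and descriptive study". All patients are treated and there is no control group. SAP section 4 says that "patients who meet the inclusion criteria are estimated to be: 10 with ATTRv and 10 with ATTRwt".
- **Methods.** NOTE 1 in SAP section 6 says that "no comparisons will be made and the associated p-value will not be shown. Only descriptive analyses will be presented".
- **Primary analysis.** SAP 12.1 refers the reader to SAP 10.3.1 at Month 12 and then adds a responder summary: "The N and % of patients responding to treatment will be calculated, defining responder as" a 12-month NIS change below 4 points. No required percentage follows.
- **Internal reference.** SAP 10.3.1 lists summary statistics. It then plans, where feasible, a paired t-test or Wilcoxon test of the rate of NIS change before against after treatment. The note to the same section keeps only the latest pre-treatment value for each patient, and SAP section 9 applies the same rule.

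Neither document gives a reference progression rate, a target mean change, a significance level or a decision rule for Month 12.

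**The concern.** A decrease in progression needs a level to decrease from. The report will show a mean 12-month NIS change and a responder percentage, and the plan does not say what value of either would support or count against the hypothesis.

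The comparator is not identified either. The Protocol background (section 7) covers slowing of neuropathy on 20 mg and also the idea that more than 20 mg may help, and Protocol 9.3 records earlier 20 mg treatment. The hypothesis could therefore mean slower than untreated or slower than on 20 mg.

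The SAP's change table (2.1) says the 12-month responder definition was added to define the primary objective, so readers are likely to take that percentage as the efficacy result. The limitations section (Protocol 9.9) mentions sample size, sparse data and other neuropathies, but not the lack of a comparator. At stake is whether a result of ordinary size is reported as efficacy when the data cannot separate it from no effect.

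**Working it through.** **Inputs.** n = 10 ATTRv (SAP section 4, a feasibility count). Patient-level cut-off: NIS change below 4 points at 12 months (SAP 12.1). The documents give no mean or SD for the 12-month change, so I assume a mean worsening m of 0 to 8 points and an SD s of 4 to 8. The plan states no power, alpha or target, so it has no figure of its own to reproduce.

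**Step 1: can the internal reference be calculated?** SAP 6.1.1 defines the monthly rate as (follow-up value − starting value) / months between them.
- Post-treatment rate: one starting value and one follow-up value, so it is available.
- Pre-treatment rate: this needs two dated values before treatment. Inclusion criterion 4 requires only one assessment, before or at the start. Protocol 9.3 plans to collect both time points, but SAP section 9 and SAP 10.3.1 keep only the latest. One value gives no rate.
- NOTE 1 forbids comparisons and p-values, while SAP 10.3.1 plans a test. Both cannot be followed.
- If the test is read instead as baseline score against Month-12 score, it asks whether NIS changed at all, not whether it worsened more slowly.
- If the test could be run in all 10 patients, 80% power at two-sided 5% (noncentral t, 9 df) would need a true difference of 0.996, or about 1.0, SD of the paired differences.

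**Step 2: precision of the responder percentage.** Exact (Clopper-Pearson) 95% limits for x of 10 are Beta(0.025; x, 11 − x) and Beta(0.975; x + 1, 10 − x).
- 5/10: 18.7% to 81.3%
- 7/10: 34.8% to 93.3%
- 9/10: 55.5% to 99.7%

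**Step 3: how far the reading depends on a benchmark.** At one-sided 0.025 with n = 10, the smallest count that exceeds an assumed benchmark is 7 for 30% (exact tail 0.0106), 8 for 40% (0.0123) and 9 for 50% (0.0107). The same 7/10 passes against 30% and fails against 40% or 50%.

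**Step 4: responder percentage with no drug effect.** For a Normal change, P(change < 4) = Φ((4 − m)/s).

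| Mean worsening m | s = 4 | s = 6 | s = 8 |
|---|---|---|---|
| 0 | 84% | 75% | 69% |
| 2 | 69% | 63% | 60% |
| 4 | 50% | 50% | 50% |
| 6 | 31% | 37% | 40% |
| 8 | 16% | 25% | 31% |

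The range is 16% to 84%, or 16% to 69% without the zero-worsening row.

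**Step 5: precision of the mean change.** The 95% half-width is t(0.975; 9) × s/√10 = 0.715 s, which is 2.86, 4.29 and 5.72 points for s = 4, 6 and 8. At SDs of 6 and 8 it exceeds the 4-point cut-off itself.

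**The case against.** The strongest defence is that this is a declared descriptive cohort of about 10 patients, with small size named as its main limitation, and that such a study does not normally need a pass mark. That stands, and it is why the remedy is to limit the claim rather than to add a hurdle. It does not remove the mismatch, because the hypothesis and objective still speak of slowing and efficacy.

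Three stronger readings are tempting, and the documents do not support them.
- **That the plan has no reference at all.** SAP 10.3.1, the section that resolves the primary objective, names each patient's own pre-treatment rate. The fault is that this reference is conditional, contradicted and not calculable as specified.
- **That any result could be presented as support.** Clear mean worsening would be hard to present that way, and so would the 16% to 31% responders in the 8-point row. The problem lies in the wide middle range.
- **That 4 points is the missing benchmark.** The ladder in SAP 12.2.1 (2, 4, 6, 8 and 12 points at 6, 12, 18, 24 and 36 months) works out at 4 points a year. It is never called an expected rate and no source is given. It classifies single patients.

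Two further points stand. The responder range in Step 4 rests wholly on assumed means and SDs, and its upper end needs zero worsening in a disease the Protocol calls progressive. SAP 3.2.1 also attaches an Archive Note to the primary objective. That note was not available, so it may hold a benchmark not seen here.

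**Conclusion.** The point holds in this form: as written, the plan cannot support or refute its own hypothesis on the primary endpoint. No benchmark is set for the Month-12 mean change or the responder percentage, and the only internal reference cannot be used under the SAP's own rules.

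The structural finding needs no assumption beyond the text. The exact intervals in Step 2 rest only on the SAP's expected 10 ATTRv patients. The 16% to 84% range also assumes Normal changes, mean worsening of 0 to 8 points and SDs of 4 to 8. It illustrates the ambiguity and does not predict what this cohort will show. The data remain useful as description. What is affected is the conclusion that can be drawn from them, so the change should be made.

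**What to change.** 1. **Restate the objective.** In Protocol section 8 and SAP 3.2.1 and 12.1, make the primary objective a description of the 12-month NIS change on 61 mg in ATTRv. State there that neither efficacy nor decreased progression will be concluded from it.
2. **Add intervals.** Report the mean change with a 95% t-interval and the responder percentage with an exact 95% interval. SAP section 6 currently lists no confidence intervals.
3. **Reconcile SAP 10.3.1 with NOTE 1.** Either delete the pre/post rate test, or keep both dated pre-treatment NIS values that Protocol 9.3 already plans to collect, run the test only in patients who have two, and label it exploratory with NOTE 1 amended to allow it.
4. **Do not turn the 4-point line into a pass mark for the group mean**, for example by requiring the upper 95% limit to lie below 4. Passing would show only that mean worsening was under 4 points, not that it was less than it would have been without 61 mg.
5. **Check the Archive Note.** If it contains a benchmark, move it into the SAP with its source.

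Cost: new wording in both documents and a few SAP lines. Data collection does not go beyond what Protocol 9.3 already plans. Changing section 8 needs a protocol amendment, and Protocol 10.3 requires ethics approval of amendments. The sponsor gives up an unqualified efficacy claim.
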